## 6.6 Prior Radiotherapy

Prior radiotherapy data will be collected at the Screening/Baseline visit.

The following data will be summarized by number and percentage of patients in each category for the Safety Analysis Set.

- Did the subject have any prior radiotherapy? (Yes/No)
- Was radiotherapy ongoing at the time of consent? (Yes/No)
- Type of radiotherapy
  - Intensity-Modulated Radiation
  - Therapy (IMRT)
  - AP-PA Therapy
  - Proton Therapy
  - Other

The following parameters will be summarized as continuous variables (N, Mean (SD) Median Min Max)

- Dose per fraction
- Number of fractions

## 6.7 Target, Non-target and New Lesions

When more than one measurable lesion is present at baseline, all lesions up to a maximum of five lesions total (and a maximum of two lesions per organ) representative of all involved organs should be identified as target lesions and will be recorded and measured at baseline. Target lesions must meet the criterion of a short axis of  $\geq 15$  mm by CT scan. All other pathological nodes (those with short axis  $\geq 10$  mm but  $< 15$  mm) should be considered nontarget lesions. Nodes that have a short axis  $< 10$  mm are considered nonpathological and should not be recorded or followed.

Sponsor: Sensi Biotherapeutics

Protocol: SNS301-2-2

The following categorical variables for target, non-target and new lesions will be summarized using descriptive statistics (number (percent))

- Site of lesion (Bone, Brain, Chest Wall, Liver, Lung, Lymph Node, Neck, Oral Cavity, Skin; Soft Tissue, Other)
- Modality (CT with Contrast, CT without Contrast, MRI)

The following continuous variables for target, non-target and new lesions will be summarized using descriptive statistics (n mean (SD), median, min, max))

- Longest Diameter
- Sum of the longest diameter (Derived)

Summaries for target, non-target and new lesions' data as assessed using iRECIST will also be presented. Data listings will also be presented for target, non-target and new lesions' data.

## 6.8 Prior and Concomitant Medications

Prior medications any prescription medications or over-the-counter medications taken or performed within 7 days prior to screening and before the first dose of study drug. At subsequent visits, changes to current medications or medications used since the last documentation of medications will be recorded.

Concomitant medications are all medications, other than the study drug, taken on or after the first day of study drug dose through 30 days after end of study medication or until the start of a new anti-cancer treatment, whichever comes first. Concomitant medications will be categorized into the following categories (listed in section 8.4 of the protocol):

- Allowed concomitant treatments
- Prohibited medications or treatments during study
- Rescue medications

Prior and concomitant medications and procedures will be coded using the World Health Organization Drug Dictionary.

- Prior and concomitant medications will be summarized by the number and proportion of the subjects who took each medication, or had qualifying concomitant procedures and will be tabulated by the ATC-2 level and preferred name. A subject will only be counted once within each ATC-2 code and within each preferred name.

Prior and concomitant medications will also be listed for Safety Analysis Set .

Sponsor: Sensi Biotherapeutics

Protocol: SNS301-2-2

## 6.9 Serology Testing Results (HIV, Hepatitis and PD-L1 Status)

If the patient's tumor's HPV/EBV status is unknown, they will be tested prior to receiving SNS-301. If the patient's tumor's PD-L1 status is unknown, they should be tested, preferably by 22C3 IHC. Patients who are CPI naïve must be PD-L1 positive prior to entry onto the study. For other patients, the results do not need to be known before the patient receives study treatment. For patients that started study treatment prior to Amendment 2/Version 3.0, retrospective PD-L1 testing should be done, whenever possible.

The results of the following tests will be summarized using descriptive statistics (Number (percent))

- HIV Testing (Positive, Negative, Unknown)
- Hepatitis B surface Testing Antigen (Positive, Negative, Unknown)
- Anti-HBc Antibody Testing (Positive, Negative, Unknown)
- Anti-HBs Antibody Testing (Positive, Negative, Unknown)
- Hepatitis C Antibody Testing (Positive, Negative, Unknown)
- PD-L1 Status (Positive, Negative, Unknown)

## 6.10 Virology Testing Results (HPV and EPV)

The results of the following tests will be summarized using descriptive statistics (Number (percent))

- HPV Status (Positive, Negative, Unknown)
- EBV Status (Positive, Negative, Unknown)

# 7. EFFICACY ANALYSIS

## 7.1 Primary Efficacy Analysis

The primary efficacy analysis will be based on the Efficacy-Evaluable Analysis Set at week 12. All efficacy variables will be presented by cohort. The following primary efficacy variables will be summarized to determine the anti-tumor activity of SNS-301:

Objective Response Rate (ORR)

- ORR is defined as the proportion of patients with a confirmed best response of iCR or iPR by iRECIST.
- ORR, and 90% CI at week 12 based on the exact binomial distribution will be presented, including number and percent of patients in each overall response category.

Sponsor: Sensi Biotherapeutics

Protocol: SNS301-2-2

- Best Overall Response ( BOR) will also be presented.

#### Disease Control Rate (DCR)

DCR is defined as the proportion of patients with SD or better (PR and CR) as assessed by RECIST version 1.1 and iRECIST. SD must be for at least six months.

- A 95% Confidence Interval based on binomial distribution will be constructed for the estimated DCR at 12 weeks.
- Subjects who drop out prior to meeting the responder criteria for DCR will be considered as non-responders.

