10.4 Statistical Analyses

The statistical analysis plan will be developed and finalized before database lock and will describe the patient populations to be included in the analyses, and procedures for accounting for missing, unused and spurious data.

The statistical analysis plan will specify how lost to follow-up patients will be addressed in the primary analysis.

10.4.1 *General Methods*

All summarizations will be presented separately for each cohort, and over all subjects combined.

For continuous variables, descriptive statistics (number (n), mean, median, standard deviation, minimum and maximum) will be presented. For categorical variables, frequencies and percentages will be presented. For time-to-event variables, percentages of patients experiencing that event will be presented and median time-to-event will be estimated using the Kaplan-Meier method. As appropriate, a 95% CI will be presented. Graphical displays will be presented, as appropriate.

Patients demographic characteristics including age, gender, and race will be analyzed, with categorical variables summarized in frequency tables while continuous variables summarized using mean (standard deviation) and median (range).

All data collected will be presented in by-patient data listings.

10.4.2 *Efficacy Analyses*

ORR is defined as the proportion of patients with a confirmed best response of iCR or iPR by iRECIST. Objective response rate will be estimated, and 90% CI based on the exact binomial distribution will be presented by cohort and overall, including number and percent of patients in each overall response category.

The primary analysis will be based on objective response at Week 12. An additional analysis of ORR based on best objective response during the study will be performed.

DOR, DCR, PFS, and OS will also be calculated, defined as follows:

- DOR: time from date of first response to date of progression, where patients without progression are censored at date of last valid disease assessment
- DCR: proportion of patients with SD or better (PR and CR). SD for at least six months
- PFS: time from date of start of treatment to date of progression, where patients without progression are censored at date of last valid disease assessment
- OS: time from date of start of treatment to date of death or censored at date of last contact

Efficacy analyses will be performed using the efficacy-evaluable analysis set.

10.4.3 *Safety Analyses*

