Stable disease duration will be measured from the time of start of treatment until the criteria for progression are met, taking as reference the smallest sum on study (including baseline).

Methods of Measurement

The same method of assessment and the same technique should be used to characterize each identified and reported lesion at baseline and during follow-up. Assessments should be identified on a calendar schedule and should not be affected by delays in therapy. While on study, all lesions recorded at baseline should have their actual measurements recorded at each subsequent evaluation, even when very small (e.g. 2 mm). If it is the opinion of the radiologist that the lesion has likely disappeared, the measurement should be recorded as 0 mm. If the lesion is believed to be present and is faintly seen but too small to measure, a default value of 5 mm should be assigned. For lesions which fragment/split add together the longest diameters of the fragmented portions; for lesions which coalesce, measure the maximal longest diameter for the “merged lesion”.

Clinical Lesions. Clinical lesions will only be considered measurable when they are superficial and ≥ 10 mm as assessed using calipers (e.g. skin nodules). For the case of skin lesions, documentation by colour photography including a ruler to estimate the size of the lesion is recommended. If feasible, imaging is preferred.

Chest X-ray. Chest CT is preferred over chest X-ray, particularly when progression is an important endpoint, since CT is more sensitive than X-ray, particularly in identifying new lesions. However, lesions ≥ 20 mm on chest X-ray may be considered measurable if they are clearly defined and surrounded by aerated lung.

CT, MRI. CT is the best currently available and reproducible method to measure lesions selected for response assessment. This guideline has defined measurability of lesions on CT scan based on the assumption that CT slice thickness is 5 mm or less. When CT scans have slice thickness greater than 5 mm, the minimum size for a measurable lesion should be twice

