## 1. PURPOSE

This Statistical Analysis Plan (SAP) describes the methods to be used in the analysis of trial data from clinical protocol 'An Open-Label, Multi-Center Trial of SNS-301 Added to Pembrolizumab in Patients with Locally Advanced Unresectable or Metastatic/Recurrent Squamous Cell Carcinoma of the Head and Neck' in order to answer the trial objective(s), and is based on the trial protocol SNS301-2-2, dated November 6, 2020 (Version 4.0).

Populations for analysis, data handling rules, statistical methods, and formats for data presentation are described within this document. The statistical analyses and summary tabulations described in this SAP will provide the basis for the results sections of the CSR for this trial. The SAP outlines any differences in data analysis methods relative to those planned in the trial protocol. Any changes to the data analysis methods after the SAP is finalized will be described in the CSR.

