#### Clinical Benefit Rate (CBR)

- CBR is defined as the proportion of patients with CR, PR or had stable disease for at least 6 Months as assessed by RECIST version 1.1 and iRECIST.
- A 95% Confidence Interval based on binomial distribution will be constructed for the estimated CBR.

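### SAP 7.1 estimates disease control at 12 weeks but counts stable disease only after six months, so the DCR estimate contradicts its own definition

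*SAP*

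**What the plan says.** **DCR.** Protocol 10.4.2 defines it as "DCR: proportion of patients with SD or better (PR and CR). SD for at least six months", with no analysis time point. SAP 7.1 keeps the six-month condition ("SD must be for at least six months") and then adds: "A 95% Confidence Interval based on binomial distribution will be constructed for the estimated DCR at 12 weeks". It also adds a drop-out rule: "Subjects who drop out prior to meeting the responder criteria for DCR will be considered as non-responders". On duration, protocol Appendix A says: "Stable disease duration will be measured from the time of start of treatment until the criteria for progression are met".

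**CBR.** The next item in SAP 7.1 states that "CBR is defined as the proportion of patients with CR, PR or had stable disease for at least 6 Months", by RECIST 1.1 and iRECIST, with a 95% interval and no 12-week qualifier. CBR is not a protocol endpoint.

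**Departures from the protocol.** SAP section 1 says "The SAP outlines any differences in data analysis methods relative to those planned in the trial protocol". The 12-week DCR is not identified as one.

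**ORR.** Protocol 10.4.2 and SAP 7.1 both require a confirmed iCR or iPR. Protocol 10.4.2 also says "The primary analysis will be based on objective response at Week 12". Four other places bear on the timing of confirmation:
- Protocol 9.1.1 describes a confirmation scan at least 4 weeks after the first response or at the next scheduled scan, in a sentence framed by RECIST 1.1.
- The footnote to the iRECIST best-response table in Appendix A assumes that confirmation is not needed.
- SAP 2.2 counts responders seen by Week 12 for the stage 1 decision.
- The duration-of-response text in SAP 7.1 refers to patients with a confirmed response at 12 weeks.

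**The concern.** DCR is listed under the primary anti-tumor objective. A rate estimated at 12 weeks cannot include patients who must first be stable for six months. A programmer who follows the SAP literally produces the CR+PR rate under the DCR label. One who follows the protocol definition produces six-month disease control. These are different numbers for the same named endpoint, and the SAP does not say which is meant.

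The ORR question is smaller. The stage 1 thresholds are 1 of 15 (Cohort A) and 2 of 15 (Cohort B), so a single response first seen at Week 12 and not yet confirmed could decide whether a cohort continues. The plan should say how such a response is handled.

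**Working it through.** **DCR: calendar check**

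Inputs: imaging every 6 weeks, ±7 days (SAP 3.3, protocol 9.1.1); stable disease counted from treatment start (protocol Appendix A); minimum duration six months (SAP 7.1, protocol 10.4.2). Neither document gives a figure for DCR to reproduce.

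- Latest Week 12 scan: 12 × 7 + 7 = 91 days.
- Six months: about 183 days, or 24 × 7 = 168 days on the shortest usual reading.
- Shortfall: 168 − 91 = 77 days at least; 183 − 91 = 92 days on the calendar reading.
- Week 24 scan: at most 168 + 7 = 175 days, short of 183. Week 30 scan: at least 210 − 7 = 203 days. So Week 30 is the first scheduled scan that can show six calendar months of stable disease; Week 24 suffices only if six months means 24 weeks.

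Stable disease on an earlier checkpoint inhibitor in Cohort A cannot fill the gap, because the clock starts with study treatment. On the literal reading the stable-disease part of the 12-week DCR is zero.

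**ORR: does the unstated rule matter?**

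The plan's own figures come first. With continuation at r1 or more responses in 15 and rejection at r or more in 30:

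- P(stop) = P(X1 < r1)
- P(reject) = Σ over x ≥ r1 of b(x; 15, p) × P(X2 ≥ r − x), with X2 ~ Bin(15, p)

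| Cohort | r1, r | Rates | Power | Type I error | Stop under null | Stop under alternative |
|---|---|---|---|---|---|---|
| A | 1, 4 | 5% / 18% | 0.8002 | 0.0582 | 0.4633 | 0.0510 |
| B | 2, 7 | 13.3% / 29% | 0.8006 | 0.0917 | 0.3881 | 0.0419 |

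These match protocol 10.2 at its stated precision (80%, 6%, 46%; 80.1%, 9.2%, 38.8%).

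Next, suppose k of the 15 stage 1 patients have reached Week 12 but not the following scan. Let f be the share of Week 12 responders who already responded at Week 6 and so are confirmed by Week 12. Responses still awaiting confirmation are left out at stage 1 and credited at the final analysis. The documents do not give f; I take 0.5 to 0.9.

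For k, planned accrual is 60 patients in 18-24 months (protocol 5.2 and synopsis): 2.5 to 3.33 per month × 42/30.44 = 3.4 to 4.6 per six weeks over both cohorts. That is about 2 per cohort if split evenly, and at most about 5 if one cohort takes all.

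| Cohort | k | False stop under alternative | Power |
|---|---|---|---|
| A | 2 | 5.3-6.3% | 79.4-79.9% |
| A | 5 | 5.7-8.6% | 78.0-79.7% |
| B | 2 | 4.5-5.7% | 79.4-79.9% |
| B | 5 | 4.9-8.8% | 77.6-79.7% |

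Each range runs over f from 0.9 to 0.5. With k = 5, the chance under the alternative that an unconfirmed response would have turned a stop into a continuation is at most 3.5% (A) or 4.6% (B). Type I error stays below the design value throughout.

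**The case against.** **On DCR.** The words *at 12 weeks* may only label the analysis set. SAP 7.1 opens by basing the primary efficacy analysis on the evaluable set at Week 12, and the same qualifier recurs under PFS, duration of response and OS. Stable-disease duration runs until progression, so it need not be cut off at the Week 12 scan. The drop-out rule also makes most sense if patients are followed to six months. This is a coherent reading and probably the intended one. It also weakens any complaint of an unannounced departure from the protocol, since carried-over wording is not a deliberate change. What it does not do is repair the text: the SAP never says this, and on this reading DCR duplicates CBR.

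A reader might infer that information on stable disease is lost from the report. The documents do not support that: CBR gives six-month disease control with an interval, and every response category is tabulated with the ORR.

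**On ORR.** SAP 2.2 and the duration-of-response text lean towards confirmation by Week 12, and protocol 10.4.2 contrasts the Week 12 analysis with a separate best-response ORR during the study. That leaning is real, but none of these places states the rule for a later confirmation, and the iRECIST table footnote points the other way. Recorded accrual is also slower than planned. Enrollment was 9 at 23 July 2020 (protocol Appendix C) and 11 at 29 October 2020 (protocol 3.1.2), which is 2 in 98 days or 2 × 42/98 = 0.9 per six weeks, all before Cohort B was added. With k = 1, Cohort A power is 79.7-80.0%.

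A reader might also infer a severe loss of power. If later confirmations were never credited, and the design rates counted responses first seen by Week 12, power would be 72%, 58% or 27% (A) and 69%, 48% or 13% (B) when 10%, 25% or 50% of responders are first seen at Week 12. The documents state neither condition. If the design rates are already confirmed Week 12 rates, nothing is lost.

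**Conclusion.** The DCR text in SAP 7.1 contradicts itself and should be corrected. The gap of at least 77 days holds whichever usual length of six months is used, and needs no assumption beyond the documents' own scan window and start of the clock. That no stable-disease patient can count is the literal reading, not a prediction of what will be programmed. The practical consequence is limited, because no decision rule uses DCR and CBR carries the same information.

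The ORR part is a clarification only. If later confirmations are credited at the final analysis, power stays at about 78-80% under the assumed 50-90% share of responses already present at Week 6 and up to 5 unconfirmed patients at the look. Whether the 5%/18% and 13.3%/29% rates are confirmed Week 12 rates is not stated. The 13.3% equals the nivolumab response rate in protocol 3.2.1.1, which is given there without a time point or confirmation basis, so neither basis can be asserted.

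**What to change.** **DCR.** Delete *at 12 weeks* from the DCR interval in SAP 7.1 and keep the six-month rule of protocol 10.4.2. DCR and CBR then have identical criteria, so report the quantity once and keep the drop-out rule with it. If a 12-week disease control rate is wanted, add it under a separate name, defined as CR, PR or SD at the Week 12 scan. The correction is one deletion plus merging two items in the SAP; it needs no protocol change and no new data.

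**ORR.** Add a sentence to SAP 7.1 and 9.5 saying whether an iCR or iPR first seen at Week 12 and confirmed at the next scheduled scan counts in the primary ORR and at stage 1. If it counts at stage 1, say whether the decision waits for that scan. The wait would be about 6 weeks (Week 12 to Week 18) and would be needed only when an unconfirmed response could change the outcome. No extra scans are required. If protocol 10.4.2 and 10.5 are aligned as well, that is an amendment needing IRB approval (protocol 11.1.1). The sponsor should check the basis of the design rates and record what is found, without declaring them confirmed rates.

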#### Clinical Benefit Rate (CBR)

- CBR is defined as the proportion of patients with CR, PR or had stable disease for at least 6 Months as assessed by RECIST version 1.1 and iRECIST.
- A 95% Confidence Interval based on binomial distribution will be constructed for the estimated CBR.

#### Progression Free Survival (PFS)

- PFS is defined as the time from date of start of treatment to date of progression or death (whichever comes first) as assessed by RECIST version 1.1 and iRECIST.
- Subjects who are alive and without documentation of progression at the time of the analysis will be censored at the date of last tumor assessment.
- Subjects with no tumor response assessment will be censored at the start date of the treatment.
- Subjects who discontinued treatment or withdrew from the study for reasons other than documented PD or death will be censored at the date of last tumor assessment prior to discontinuation or withdrawal.
- PFS rate at 12 weeks and the corresponding 95% CIs will be calculated based on Kaplan-Meier product limit estimates and will be displayed along with the corresponding number of subjects at risk.
- The 25th percentile, Median, and 75th percentile of PFS as well as the corresponding 95% confidence limits will be estimated using Kaplan-Meier method. Number of patients with PD, number of deaths and number censored will be presented.
- Kaplan-Meier curves of PFS by cohort will be displayed graphically.

#### Overall Survival (OS)

- OS is defined as time from date of start of treatment to date of death.
- OS rate at 12 weeks and the corresponding 95% CIs will be calculated and summarized based on Kaplan-Meier product limit estimates and will be displayed along with the corresponding number of subjects at risk.
- Subjects who are still alive will be censored on the date of last contact.
- The 25th percentile, Median, and 75th percentile of OS as well as the corresponding 95% confidence limits will be estimated using Kaplan-Meier method. Number of patients who died and number censored will be presented.
- Kaplan-Meier curves of OS by cohort will be displayed graphically.

### 7.2 Secondary Efficacy Analysis

To determine preliminary immune response to SNS-301, the following parameters will be assessed:

- Antigen-specific cellular immune responses that may be assessed by but not limited to: Interferon- $\gamma$  secreting T lymphocytes in peripheral blood mononuclear cells (PBMCs) by ELI Spot
- Anti-SNS-301 antibody secretion
- Assessment of pro-inflammatory and immunosuppressive elements in neoplastic and adjacent normal tissue, where feasible

Categorical results will be summarized using the number (percent) format and continuous results will be presented in the n, mean(SD), median, min and max format.

### 7.3 Exploratory Efficacy Analysis

Sponsor: Sensi Biotherapeutics

Protocol: SNS301-2-2

To determine tumor and immune biomarkers and their association with treatment outcome (antitumor activity and/or safety) in patients with locally advanced unresectable or metastatic/recurrent SCCHN, the following parameters will be assessed:

- Immune related gene expression
- Expression of tumor specific oncoproteins including but not limited to ASPH
- Correlation of serum ASPH level as determined by ELISA with tissue expression using IHC
- Cytokine and chemokine profiles in urine pre- and post-treatment and longitudinally throughout the trial
- TCR sequencing of PBMCs for diversity and putative antigen specificity
- CtDNA analysis and tracking for progression

Categorical results be summarized using the number (percent) format and continuous results will be presented in the n, mean(SD), median, min and max format.

